**STUDY SUMMARY:**

Investigational Agent(s) (Drugs or Devices)	Active Treatment: Low Dose Quadruple Combination Therapy (LDQT) comprising candesartan 2 mg, amlodipine 1.25 mg, indapamide 0.625 mg, and bisoprolol 2.5 mg Comparator: Candesartan 8 mg
IND / IDE / HDE #	133846
Indicate Special Population(s)	 Children  Children who are wards of the state  Adults Unable to Consent  Cognitively Impaired Adults  Neonates of Uncertain Viability  Pregnant Women  Prisoners (or other detained/paroled individuals)  Students/Employees
Sample Size	87
Funding Source	National Heart, Lung, and Blood Institute
Indicate the type of consent to be obtained	 Written  Verbal/Waiver of Documentation of Informed Consent  Waiver of HIPAA Authorization  Waiver/Alteration of Consent Process
Site	 Lead Site (For A Multiple Site Research Study)  Data Coordinating Center (DCC)
Research Related Radiation Exposure	 Yes  No
DSMB / DMC / IDMC	 Yes  No

**ABBREVIATIONS:**

ABPM	Ambulatory Blood Pressure Monitoring
ACE-I	Angiotensin-converting-enzyme inhibitor
AE	Adverse Event
ALP	Alkaline Phosphatase, a kind of enzyme
ALT	Alanine Transaminase, a kind of enzyme
ARB	Angiotensin II receptor blocker
AST	Aspartate Aminotransferase, a kind of enzyme
BB	Beta Blocker
BMI	Body Mass Index
BP	Blood Pressure
CABG	Coronary Artery Bypass, a type of surgery that improves blood flow to the heart
CAD	Coronary Artery Disease
CCB	Calcium Channel Blocker
CRF	Case Report Form
DBP	Diastolic Blood Pressure
DSMB	Data and Safety Monitoring Board
DSMP	Data and Safety Monitoring Plan
ECG/EKG	Electrocardiogram
eConsent	Electronic consent
ECT	Electroconvulsive Therapy, a medical treatment used in patients with severe major depression
eGFR	Estimated Glomerular Filtration rate, a number based on the creatinine level in the blood
GCP	Good Clinical Practice
GGT	Gamma-Glutamyl Transferase, a kind of enzyme found in many organs throughout the body
HDL	High Density Lipoprotein, a group of lipoproteins that transport all fat molecules around the body in the extracellular water
IPD	Individual Participant Data
LVH	Left Ventricular Hypertrophy, a term for a heart's left pumping chamber that has thickened and may not be pumping efficiently
MI	Myocardial Infarction, a kind of heart attack
PCI	Percutaneous Coronary Intervention, a non-surgical procedure to treat narrowing of the coronary arteries
PROMIS	Patient-reported Outcome Measurement Information System
QRS	The main spike seen on an ECG line
QTc	The interval that represents the total time from ventricular depolarization to complete repolarization
SAE	Serious Adverse Event
SBP	Systolic Blood Pressure
TIA	Transit Ischemic Attack, a brief stroke-like attack that can be resolved within minutes to hours
UACR	Urine Albumin: Creatinine Ratio

## 1. OBJECTIVES

To investigate, in a double-blind randomized controlled trial, whether initiating treatment with ultra-low-dose quadruple-combination therapy (“LDQT”) will lower office blood pressure more effectively, and with fewer side effects, compared to initiating standard dose monotherapy in patients with hypertension.

Primary hypothesis: A combination pill comprising four types of blood pressure lowering medications, each at one-quarter standard doses, will lower office blood pressure more effectively than initiating patients with standard dose monotherapy in patients with hypertension.

## 2. BACKGROUND

### 2.1. Burden of raised blood pressure and treatment gaps

Elevated blood pressure, also known as hypertension when  $\geq 130/\geq 80$  mmHg, is a leading cause of preventable morbidity and mortality globally. In the United States, approximately 45.6% of adults, or 103.3 million individuals have hypertension, and prevalence rates are rising, particularly among non-Hispanic black men and women in whom prevalence rates exceed 50%. Among Americans with elevated blood pressure, 81.9 million are eligible for pharmacotherapy based on the 2017 AHA/ACC blood pressure guideline, an absolute increase of 4.2 million Americans compared with previous thresholds for initiation of pharmacotherapy ( $\geq 140/\geq 90$  mmHg). The benefits of blood pressure lowering in reducing cardiovascular events are unequivocal. Blood pressure lowering therapy leads to an estimated 11% reduction in all-cause mortality (relative risk [RR] = 0.89 [95% CI 0.85, 0.95]), 16% reduction in coronary heart disease events (RR = 0.84 [95% CI 0.79, 0.90]), and 36% reduction in stroke (RR = 0.64 [95% CI 0.56, 0.73]). The typical estimated blood pressure lowering effect from a standard dose of a single drug ranges from 6-9/3-6mmHg. Therefore, improving blood pressure control is a strategic priority for reducing the burden of cardiovascular disease in the United States and around the world.

While most Americans are aware of their hypertension and while most of those who are aware receive treatment (75%), less than half (47%) are controlled using a goal blood pressure of  $<130/\geq 80$  mmHg when using nationally representative data (compared with 52% based on the previous target of  $<140/\geq 90$  mmHg). These recommendations were based on high-quality data from the Systolic Blood Pressure Intervention Trial (SPRINT), yet the method of implementing this strategy, which includes repeated clinic visits with repeated dose titrations of individual drugs, is challenging. This strategy is also limited because maximizing doses of individual drugs leads to a greater risk of side effects without a similar benefit to blood pressure reduction.

This proposal aims to substantially simplify and improve the efficacy and safety of blood pressure-lowering treatment by changing the initial treatment paradigm for patients with essential hypertension who are eligible for pharmacotherapy without prevalent cardiovascular disease. We hope to change the treatment paradigm from moderate dose, single-drug therapy with repeated dose titration to ultra-low dose, quadruple combination therapy (LDQT). Combination therapy improves adherence in many chronic conditions, including elevated blood pressure and cardiovascular diseases, but it has been typically reserved for individuals with very high (systolic blood pressure [SBP]  $>150$  mmHg in the 2017 guideline compared with  $>160$

mmHg in previous guidelines) or difficult to control blood pressures. The proposed treatment regimen has the potential to make it easier for typical patients and clinicians to achieve blood pressure goals with fewer pills and fewer clinic visits to prevent fatal and non-fatal cardiovascular disease events and to improve cardiovascular health with a focus on vulnerable groups who bear a disproportionate burden of hypertension and hypertension-related diseases.

## **2.2. Barriers to hypertension control**

There are multiple barriers to hypertension control, including patient-and physician-related factors. Patient adherence is a major factor in hypertension control and is worsened by increased number of medications, complexity of dosing regimens, and medication side effects. “Therapeutic inertia”, which is the reluctance of clinicians to treat “mild” hypertension (SBP <160 mmHg) despite demonstrated benefits or to up-titrate medications, remains an important barrier to hypertension control. Current guidelines typically recommend initiating monotherapy, up-titration, switching drugs if not tolerated, and adding other agents if needed. This strategy often takes multiple visits to achieve blood pressure goals, which results in most patients remaining on monotherapy with inadequate blood pressure control. SPRINT participants randomized to a SBP goal <120 mmHg took, on average, three pills at standard dose for blood pressure control compared with two pills at standard dose among individuals randomized to the SBP goal <140 mmHg. Translating these important research findings into routine clinical practice, particularly among vulnerable populations, will be difficult using the current paradigm of blood pressure management.

## **2.3. Combination therapy for blood pressure lowering**

Because 50% to 75% of patients require multi-drug treatment for blood pressure control, there has been increasing interest in the initial use of combination therapy. A 2013 survey of 31 international hypertension guidelines demonstrated that 27 (87%) of guidelines recommend use of combination for initial treatment but typically only as an option for patients at >20/10 mmHg from goal, which is concordant with the 2017 AHA/ACC blood pressure guideline. Nevertheless, there is evidence of improved adherence for combination-based therapy (albeit typically two drug combinations) compared to monotherapy for treatment of elevated blood pressure, cardiovascular diseases, and other chronic conditions with estimates ranging from 25% to 50%. Most recently, the TRIple pill vs. Usual care Management for Patients with mild-to-moderate Hypertension (TRIUMPH) trial evaluating half-dose, triple drug combination (telmisartan 20 mg, amlodipine 2.5 mg, chlorthalidone 12.5 mg) demonstrated hypertension control rates of 70% in the intervention compared with 55% in the usual care arm at six months among 700 adults in Sri Lanka.

While these data are promising for the use of low-dose combination therapy for the treatment of mild and moderate hypertension, they need further study with an active comparator arm to reduce the risk of performance bias and within a broader, more diverse population.

Combinations with more drugs but at lower doses (four drugs at quarter doses) than what was used in TRIUMPH (three drugs at half doses) may be even more effective and with a better side effect profile. Therefore, there is a clear need for improved strategies to: 1) make treatment of hypertension more effective and easier to implement for patients and clinicians, 2) quickly and

safely bring elevated blood pressure to lower goals than those recommended in the past, and 3) increase long-term adherence with therapy.

In August 2021, the QUARTET (Australia) trial compared the effect of irbesartan at 37.5 mg, amlodipine at 1.25 mg, indapamide at 0.625 mg, and bisoprolol at 2.5 mg with irbesartan 150 mg daily among 591 patients with mild to moderate hypertension who had a baseline mean (SD) systolic blood pressure of 142 (13) mmHg in the intervention group and 140 (13) mmHg in the control group. Compared with the irbesartan control group, patients randomized to the quadpill had a 6.9 mmHg (95% CI: 4.9-8.9) greater systolic blood pressure lowering at 12 weeks. These results were sustained up to 12 months in a sample of 417 patients who were followed for 12 months when the difference was 7.7 mmHg (95% CI: 5.2-10.3) of systolic blood pressure. Dizziness was reported among 93 (31.0%) patients in the intervention group compared with 74 (25.4%) patients in the control group (RR 1.27 [95% CI: 0.98-1.64]). There were no serious adverse events due to syncope, falls, or acute kidney injury. The study participants were largely White (82%) and Asian (12%) race/ethnicity. Thus, there is promising evidence of an ultra-low-dose combination approach, but additional data are needed in more diverse populations.

### **3. STUDY ENDPOINTS**

#### **3.1. Primary**

Mean change (from baseline) in automated office SBP at 12 weeks adjusted for baseline values.

#### **3.2. Secondary**

1. Mean automated office SBP at 12 weeks adjusted for baseline values.
2. Other blood pressure measures in active vs. control groups (adjusted for baseline values in each case):
  - a. Mean change (from baseline) in automated office SBP at six weeks.
  - b. Mean automated office SBP at six weeks.
  - c. Mean change (from baseline) in automated office DBP at six and 12 weeks.
  - d. Mean automated office DBP at six and 12 weeks.
  - e. Proportion of patients with hypertension control (percent with SBP < 130 mmHg and DBP < 80 mmHg) at six and 12 weeks.
  - f. Proportion of patients requiring step-up treatment (ever, and at each study time point).
  - g. Proportion of patients with adverse event-free hypertension control (percent with SBP < 130 mmHg and DBP < 80 mmHg).
3. Medical adherence:
  - a. Medication adherence defined by objective pill counts.
4. Health-related quality of life:
  - a. Mean change (from baseline) in health-related quality of life using PROMIS Global Health instrument.

### 3.3. Tolerability & Safety

- a. Percentage of participants with any SAE according to GCP definition.
- b. Percentage of participants with any potentially relevant side effect (refer to the adverse event case report form and the list of relevant side effects from the informed consent form, included as an Appendix).
- c. Rate of relevant side effects at the participant level.
- d. Mean change (from baseline) in continuous serum potassium (mEq/L).
- e. Mean change (from baseline) in continuous serum sodium (mEq/L).
- f. Mean change (from baseline) in continuous blood urea nitrogen (mg/dl).
- g. Mean change (from baseline) in continuous serum creatinine (mg/dl).

### 3.4. Exploratory

1. 24-hour ambulatory blood pressure measures
  - a. Mean 24-hour SBP and DBP assessed through 24-hour ambulatory blood pressure monitoring.
  - b. Mean daytime (0600 to 2200) SBP and DBP assessed through 24-hour ambulatory blood pressure.
  - c. Mean nighttime (2200 to 0600) SBP and DBP assessed through 24-hour ambulatory blood pressure.
  - d. Proportion of dippers\* assessed through 24-hour ambulatory blood pressure.
  - e. Mean daytime SBP and DBP load assessed through 24-hour ambulatory blood pressure. Load is defined as the percentage of abnormally elevated readings; daytime SBP / DBP elevated readings would be 130 / 80 mmHg or above.
  - f. Mean nighttime SBP and DBP load assessed through 24-hour ambulatory blood pressure. Abnormally elevated readings for nighttime SBP / DBP would be 120 / 70 mmHg or above.
  - g. Percentage of participants with morning surge, calculated as the difference between the mean SBP during the morning hours and nighttime trough SBP. Trough SBP was defined as the mean of three SBP measurements: the lowest nighttime SBP and the measurements immediately preceding and following this measurement.
  - h. Coefficient of variation of SBP and DBP assessed through 24-hour ambulatory blood pressure as defined as the ratio of the 24-hour standard deviation of BP / mean 24-hour value.
  - i. Day-night variability (SDdn), which uses the SD for daytime measurements and, separately for nighttime measurements, to calculate a weighted mean of these SDs.
  - j. Average real variability (ARV), which is calculated as the average absolute difference between consecutive readings over the 24-hour ABPM period.
  - k. Additional exploratory outcomes will be assessed as needed to inform individual participant data (IPD) meta-analysis with international QUARTET studies.

\*Dipping is defined as nighttime blood pressure falling more than 10% from the daytime values OR night / day blood pressure ratio less than 0.9 and greater than 0.8 with normal diurnal blood pressure pattern.

#### **4. STUDY INTERVENTION**

Patients who are eligible to participate in the trial will be randomized (1:1 allocation) to one of two study arms, and they will take daily:

1. Low Dose Quadruple Therapy (LDQT) comprising candesartan 2 mg, amlodipine 1.25 mg, indapamide 0.625 mg, and bisoprolol 2.5 mg  
OR
2. Candesartan 8 mg

The LDQT includes quarter standard doses of four blood pressure lowering medications, which are currently approved by the US Food and Drug Administration for the treatment of hypertension. The active comparator follows current clinical practice guidelines for the majority of Americans, initiating treatment with an angiotensin II receptor blockers (ARB), which has the best side effect profile of any blood pressure lowering therapy. In both arms, if blood pressure is not controlled (SBP > 130 mmHg or DBP > 80 mmHg) at the six-week follow-up assessment, then study staff will provide participants with an open label pill of amlodipine 5 mg to supplement their study drug, which may be relevant to participants from some race/ethnic groups, including African-Americans. The combination of a calcium channel blocker with an ACE-inhibitor has been demonstrated to be more effective in reducing cardiovascular events than the combination of a thiazide-like diuretic with an ACE-inhibitor based on the ACCOMPLISH trial.

All study drugs, including LDQT, active comparator, and amlodipine add-on will be stored, controlled, and administered centrally. Control of drugs is described in full in the detailed Manual of Procedures. Drug product used in this study is subject to regulatory review and approval through an investigator-initiated investigational new drug (IND) process. Prior to use in human subjects, IND approval will be required.

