## **25. MULTI-SITE OR COLLABORATIVE RESEARCH:**

Northwestern investigators will collaborate with the research team at Washington University in St. Louis and Access Community Health Network. Study procedures will occur at the Access Community Health Network, where informed consent will be sought and study procedures will be conducted. The Northwestern IRB will serve as the IRB of record, and no activities will occur at Washington University in St. Louis until the SMART IRB LOA reliance agreement has been fully executed and appropriate local regulatory processes are followed and completed. The project is federally funded. The IRB approved the initial protocol before the Cooperative Research Requirement effective date. A single IRB is not required but is permissible.

Northwestern University has served as the prime institution since the study start in 2018. As of January 2022, the prime institution will be Washington University in St. Louis based on the institutional change by the contact mPI, [name]. Enrollment will be completed in May 2022. The Access Community Health Network has agreed for Northwestern to serve as the IRB of record in accordance with their local policies.

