2. STUDY OUTCOMES

In the sections below, we include the relevant specific field names for variables within the study database as of the time of SAP creation. These are indicated by the [brackets].

Primary Outcome

Primary efficacy outcome is **mean change (from baseline) in automated office systolic blood pressure (SBP) at 12 weeks** [sbpavg], and analyses will compare this change across arms for primary outcome analyses, adjusting for baseline.

Secondary Outcomes

Secondary efficacy outcomes include:

- 1) Mean automated office SBP at 12 weeks, adjusted for baseline values [sbpavg].
- 2) **Other BP measures** that will be compared across arms, controlling for baseline values:
 - a. Mean change (from baseline) in automated office SBP [sbpavg] at six weeks.
 - b. Mean automated office SBP [sbpavg] at six weeks.
 - c. Mean change (from baseline) in automated office DBP [dbpavg] at six and 12 weeks.
 - d. Mean automated office DBP [dbpavg] at six and 12 weeks.
 - e. Proportion of patients with hypertension control (SBP < 130 mmHg and DBP < 80 mmHg) at six and 12 weeks [sbpavg, dbpavg].
 - f. Proportion of patients requiring step-up treatment [amlo_dispnd].
 - g. Proportion of patients with adverse event-free hypertension control (SBP < 130 mmHg and DBP < 80 mmHg [sbpavg, dbpavg]). For the purposes of this outcome, we will define adverse event-free as absence of any events that are documented as either possibly, probably, or definitely related to study medication ([saerelate] = 3, 4, 5).
- 3) **Medication adherence:** proportion of participants deemed adherent to study medication based on the 80% criterion (i.e., participant took at least 80% of assigned study medication). This information will be captured via:
 - a. Objective pill counts [capsret6, lost6, capsret12, lost12], and
 - b. Self-reported measures [forget, miss30, miss7] in addition to the objective pill counts.
- 4) **Health-related quality of life:** Mean change from baseline in health-related quality of life

using PROMIS Global Health instrument [global01—global10]. There are two domains within this construct:

- a. Global Mental Health (assessed via a T-score)
- b. Global Physical Health (assessed via a T-score)

Safety Outcomes

We plan to evaluate the following safety outcomes:

- 1) Proportion of participants with *any* SAE according to the Good Clinical Practice (GCP) definition [sae_present, saedeath, saelifethrt, saehosp, saedisp, saecong, saeimpevnt].

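### Protocol section 4 triggers add-on amlodipine only above 130 or above 80 mmHg, but the control endpoint already counts 130 or 80 as uncontrolled, so some boundary readings get no step-up

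*Protocol*

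**What the plan says.** Protocol section 4 sets the dosing rule for both arms at week 6. The condition for adding treatment reads "if blood pressure is not controlled (SBP > 130 mmHg or DBP > 80 mmHg) at the six-week follow-up assessment". When a participant meets it, the add-on is amlodipine 5 mg, given unblinded on top of the randomized drug. Both inequalities are strict, so exactly 130 systolic or exactly 80 diastolic does not trigger the add-on on its own.

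The secondary endpoint is also strict, but in the opposite direction. Protocol section 3.2 lists "Proportion of patients with hypertension control (percent with SBP < 130 mmHg and DBP < 80 mmHg) at six and 12 weeks", and SAP section 2 repeats it: "Proportion of patients with hypertension control (SBP < 130 mmHg and DBP < 80 mmHg) at six and 12 weeks". Under that definition exactly 130 or exactly 80 is uncontrolled.

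Elsewhere the boundary also falls on the elevated side. Protocol section 2.1 places hypertension at 130 or above systolic and 80 or above diastolic. For daytime ambulatory load, Protocol section 3.4 states that "daytime SBP / DBP elevated readings would be 130 / 80 mmHg or above". Protocol section 9.1 accepts a clinic SBP of 130 for entry in a patient on monotherapy.

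The proportion needing step-up is itself a secondary outcome (Protocol section 3.2). SAP section 2 takes it from the amlodipine-dispensed field.

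**The concern.** Section 4 does not present its threshold as a separate treatment trigger. It describes blood pressure as not controlled and defines that in parentheses. The protocol therefore carries two definitions of one term for one visit, and gives no reason for the difference.

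The threshold decides who receives an additional active drug for the second half of follow-up. Three things depend on it:

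- **The step-up outcome.** Participants on the boundary are counted as not needing step-up while the endpoint scores them as uncontrolled at the same visit.
- **The 12-week blood pressure and control outcomes.** Boundary participants reach week 12 without the add-on that someone 1 mmHg higher receives.
- **The exploratory strata in SAP section 6** (analyses contingent on add-on therapy). These would place the same participants among those who did not require add-on.

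Week-6 control is measured before any add-on is given, so it is not affected.

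**Working it through.** **1. The logic, with no distributional assumptions.** Set the section 4 trigger (SBP > 130 or DBP > 80) against the complement of the endpoint (SBP ≥ 130 or DBP ≥ 80) for the nine pairs around the boundary.

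| SBP/DBP | Endpoint | Section 4 trigger | In the gap |
|---|---|---|---|
| 129/79 | controlled | no | no |
| 129/80 | uncontrolled | no | **yes** |
| 129/81 | uncontrolled | yes | no |
| 130/79 | uncontrolled | no | **yes** |
| 130/80 | uncontrolled | no | **yes** |
| 130/81 | uncontrolled | yes | no |
| 131/79 | uncontrolled | yes | no |
| 131/80 | uncontrolled | yes | no |
| 131/81 | uncontrolled | yes | no |

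In general the gap is SBP = 130 with DBP ≤ 80, or DBP = 80 with SBP ≤ 130. With the trigger at ≥ 130 or ≥ 80 the gap is empty.

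**2. How many people.** The documents give no figure to reproduce, so this step is illustrative.

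From the documents: 87 randomized and an office SBP standard deviation of 15 mmHg (Protocol section 16.1), and baseline SBP standard deviations of 13 mmHg in the Australian trial (Protocol section 2.3).

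Assumed: week-6 SBP mean 128 to 133 (SD 13 to 15), DBP mean 79 to 82 (SD 9 to 10), SBP–DBP correlation 0.55, bivariate normal. The documents do not say whether averaged pressures are kept in whole mmHg or to fractions, so both are shown. Thirds would arise from averaging three readings.

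P(gap) = P(SBP ≤ 130 and DBP ≤ 80) − P(SBP < 130 and DBP < 80)

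On a grid of width w this is Φ₂(130 + w/2, 80 + w/2) − Φ₂(130 − w/2, 80 − w/2), with w = 1 or w = 1/3. Φ₂ is the joint normal distribution function of SBP and DBP.

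| Week-6 SBP mean (SD), DBP mean (SD) | Whole mmHg | Of 87 | Thirds | Of 87 |
|---|---|---|---|---|
| 128 (13), 79 (9) | 41.66% − 37.71% = 3.95% | 3.4 | 1.32% | 1.1 |
| 130 (14), 80 (9.5) | 36.04% − 32.52% = 3.52% | 3.1 | 1.17% | 1.0 |
| 133 (15), 82 (10) | 28.19% − 25.21% = 2.98% | 2.6 | 0.99% | 0.9 |

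A simulation of three whole-number readings in 1,000,000 people agrees: 3.96%, 3.53% and 2.99% with a rounded mean, and 1.32%, 1.16% and 0.98% with thirds. In the rounded case 6.4 to 7.3% of people have SBP = 130 or DBP = 80, and only about half of them are in the gap. The rest are stepped up through the other component.

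On a wider grid (SBP mean 126 to 135, DBP mean 77 to 82, correlation 0.4 to 0.7) the ranges are 2.7 to 4.1% and 0.9 to 1.4%.

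**3. Effect on the step-up outcome.** In the middle scenario, moving from > to ≥ raises the share stepped up from 64.0% to 67.5% (whole mmHg) or from 65.1% to 66.3% (thirds).

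**4. Effect on 12-week SBP.** Protocol section 2.1 states: "The typical estimated blood pressure lowering effect from a standard dose of a single drug ranges from 6-9/3-6mmHg". Applying the full systolic effect to everyone in the gap gives the most an arm mean could move:

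- lower end: 0.9% × 6 = 0.05 mmHg
- upper end: 4.1% × 9 = 0.37 mmHg

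The direction is the same in both arms.

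**The case against.** The strongest reply is that a treatment trigger and a responder endpoint need not be exact complements. Withholding amlodipine at exactly 130 or 80 is workable, and no endpoint is left ambiguous. Control is defined identically in both documents, step-up is read from what was dispensed, and each can be computed without the other. That would settle the matter if section 4 had described a separate trigger. It instead labels the trigger as blood pressure that is not controlled, so the protocol conflicts with its own definition.

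The objection on size stands. The primary outcome is a between-arm contrast, so a shared shift largely cancels. Even if the two arms sat at opposite ends of the whole-mmHg scenarios, the contrast would move by (3.95% − 2.98%) × 9 = 0.09 mmHg, against a design difference of 5 mmHg.

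Three narrower points also stand:

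- The ambulatory load definition concerns a different measurement, and section 2.1 is not consistent in its notation: it also prints a treatment goal with ≥ 80 for diastolic. The case rests on section 4 against the control endpoint.
- The Manual of Procedures was not available. It may state the boundary and rounding rule that staff used, so the gap is what the protocol text implies and is not established practice.
- A late amendment would mix two trigger rules within the step-up outcome.

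**Conclusion.** The concern holds. Section 4 contradicts the plan's own definition of control at the week-6 visit, and that conclusion needs no assumptions. Its size does: about 1 to 4 of 87 participants, given the assumed week-6 means, standard deviations and correlation, and depending on how averages are recorded. The consequences are confined to the step-up outcome and, slightly, to 12-week blood pressure and control in the few people affected. Sample size, power and type I error do not change. The rule is identical in two blinded arms, so no between-arm bias is shown. It is a small error in a dosing rule and should be corrected.

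**What to change.** In Protocol section 4, change the trigger to SBP ≥ 130 mmHg or DBP ≥ 80 mmHg, which is the exact complement of the control definition. Protocol section 3.2 and SAP section 2 already agree with each other and need no change.

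The cost is one small protocol amendment to a dosing rule under an IND. Timing limits its value. Protocol section 25 states "Enrollment will be completed in May 2022", and the last week-6 visits would follow about six weeks after that. An amendment in that period reaches only the remaining participants and leaves earlier ones treated under the old boundary. If it is too late to amend, state in the SAP and the report which rule was applied, and give the number of participants per arm whose week-6 reading fell in the gap.
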